4.1. Primary End Points + Time Points

To measure the effectiveness of sargramostim on restoring lung homeostasis, the **primary endpoint** of this intervention is **measuring oxygenation** after 5 DAYS of inhaled (and intravenous) treatment through assessment of pretreatment (day 0) and post-treatment (day 5) ratio of PaO₂/FiO₂ and through measurement of the P(A-a)O₂ gradient, which can easily be performed in the setting of clinical observation of patients admitted to the COVID -19 ward or ICU COVID-19 unit. Preferentially, this measurement should be done in the upright position, while breathing room air for a minimum of 3 minutes. If this is impossible due to need for supplemental oxygen, FiO₂ and oxygen supplementation method should be recorded in patient record, so that A-a gradient can be normalized for age expected normal A-a gradient while on supplemental oxygen use.

During the 5 day treatment period, we will perform daily measurements of oxygen saturation (pulse oximetry) in relation to FiO₂, and the slope of alterations in this parameters could also be an indicator that our hypothesis is correct.

If the patient leaves hospital prior to the day 6 analysis point, oxygenation at day of discharge will be used as value for measuring primary endpoint.

Improvement will be expressed as % of patients showing an improvement in $P(A-a)O_2$ gradient and PaO_2/FiO_2 ratio between day 6 and day 1 of at least 25%; at least 33% and at least 50% in each treatment arm and expressed also as mean and median change in $P(A-a)O_2$ gradient and PaO_2/FiO_2 ratio comparing D6 to D1 in both treatment arms.

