Dosing of inhaled and systemic sargramostim are based on prior experience of this drug in patients with pulmonary alveolar proteinosis (inhaled) and with pneumonia associated ARDS (inhaled and intravenous). The inhaled route is preferred first, because high local concentrations of GM-CSF have a favourable effect on lung immunity, lung homeostasis and lung repair. The switch to intravenous treatment with deterioration requiring initiation of mechanical ventilation is necessitated by the fact that patients with COVID-19 poorly tolerate ventilation in the absence of high level positive end expiratory pressure (PEEP), especially when they develop ARDS. For giving the sargramostim via inhalator in a ventilated patient, this would involve PEEP-free ventilation for at least 10-15 minutes, which will not be tolerated in COVID-19 associated severe hypoxic respiratory failure and/or ARDS according to expert opinion ([name]. [name], Intensive Care Unit, UZ Ghent).

To measure the effectiveness of sargramostim on restoring lung homeostasis, the **primary endpoint** of this intervention is **measuring oxygenation** after 5 days of inhaled (and intravenous) treatment through assessment of pretreatment and post-treatment ratio of PaO₂/FiO₂ and through measurement of the P(A-a)O₂ gradient, which can easily be performed in the setting of clinical observation of patients admitted to the COVID -19 ward or ICU COVID-19 unit. Supplemental oxygen use will be recorded, and if needed A-a gradient will be normalized against expected age- and supplemental oxygen dependent A-a gradient. During the 5 day treatment period, we will perform daily measurements of oxygen saturation (pulse oximetry) in relation to FiO₂, and the slope of alterations in this parameters could also be an indicator that our hypothesis is correct. If the patient leaves hospital prior to the day 6 analysis point, oxygenation at day of discharge will be used as value for measuring primary endpoint.

Comparison will be between active group A receiving sargramostim on top of standard of care and control group B receiving standard of care.

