12.2. Type of statistical methods

All endpoints will be summarized and where relevant represented graphically

A detailed statistical analysis plan (SAP) has been set up by EffectStats LLC, Cambridge Massachusetts, USA. The statistical tests to be used to look at improvements in oxygenation between treatment groups will be a Chi-square test. Mortality frequencies will be analyzed using Wald test.

Key timepoints of interest for endpoints include Day 6 and Day 11, where data are available. All available efficacy data will be tabulated and presented for all patients in the mITT Population.

Oxygenation after 5 days of Sargramostim Intervention

To measure the effectiveness of sargramostim on restoring lung homeostasis, the primary endpoint of this intervention is measuring oxygenation after 5 days of inhaled (and intravenous) treatment through assessment of pretreatment and post-treatment ratio of $\text{PaO}_2/\text{FiO}_2$, $\text{SpO}_2/\text{FiO}_2$ and through measurement of the P(A-a)O_2 gradient. During the 5 day treatment period, daily measurements of oxygen saturation (pulse oximetry) in relation to FiO_2 will be performed. Negative value of P(A-a)O_2 gradient would be removed from the primary analysis.

P(A-a)O_2 gradient, $\text{PaO}_2/\text{FiO}_2$ ratio and $\text{SpO}_2/\text{FiO}_2$ are defined as:

$\text{P(A-a)O}_2 \text{ gradient} = [(\text{FiO}_2) \times (\text{Atmospheric Pressure} - \text{H}_2\text{O Pressure}) - (\text{PaCO}_2/0.8)] - \text{PaO}_2$

$\text{PaO}_2/\text{FiO}_2 = \text{Partial Pressure Oxygen/Fraction of Inspired Oxygen} \times 100$

$\text{SpO}_2/\text{FiO}_2 = \text{Oxygen Saturation/ Fraction of Inspired Oxygen} \times 100$

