Comparison will be between active group A receiving sargramostim on top of standard of care and control group B receiving standard of care. The change from baseline and daily change from baseline in oxygenation/respiratory parameter of P(A-a)O_2 gradient, ratio of $\text{PaO}_2/\text{FiO}_2$ and ratio of $\text{SpO}_2/\text{FiO}_2$ will be evaluated and summarized between group A and group B at Day 6. The difference of change from baseline between two groups will be tested by a t-test. In general, the last observed measurement prior to the first dose of study treatment occurred on Day 1 visit will be considered the baseline measurement. Day 6 is the primary analysis point. If the patient leaves hospital prior to the day 6 analysis point, oxygenation at day of discharge will be used as value for measuring primary endpoint.

The analyses described above will also be performed between group A (early 5 day intervention with sargramostim) and group D (late 5 day intervention with sargramostim). Change from baseline (D1) to Day 10, daily change from baseline (D1) at Day 10 in oxygenation/respiratory parameter of P(A-a)O_2

gradient, ratio of $\text{PaO}_2/\text{FiO}_2$ and ratio of $\text{SpO}_2/\text{FiO}_2$ will be summarized as well. A t-test will be conducted to compare the difference between the groups.

The same analyses will be repeated for pathological oxygenation parameter of P(A-a)O_2 gradient, ratio of $\text{PaO}_2/\text{FiO}_2$ and ratio of $\text{SpO}_2/\text{FiO}_2$ including summary of their value and change from baseline at Day 6 and Day 10. A waterfall plot will be used to represent the change from baseline and percentage change from baseline on Day 6 for 1) oxygenation parameter of P(A-a)O_2 gradient; 2) pathological oxygenation parameter of P(A-a)O_2 gradient; 3) ratio of $\text{PaO}_2/\text{FiO}_2$; 4) ratio of $\text{SpO}_2/\text{FiO}_2$. Percentage change from baseline of P(A-a)O_2 gradient and ratio of $\text{PaO}_2/\text{FiO}_2$ on Day 6 and follow-up will be summarized.

Reasons of missing AA gradient values on Day 6 will also be summarized.

The normal value of AA gradient for room air is calculated as: $2.5 + (0.21 \times \text{Age})$. All the results including change from baseline, and maximum change from baseline after 5 day intervention with sargramostim, normal AA gradient value for room air and flag of abnormality on Day 6 will be listed.

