At least 25% reduction from baseline, at least 33% reduction from baseline, and at least 50% reduction from baseline in P(A-a)O_2 gradient and pathological gradient on Day 6 will be summarized for mITT population.

Survival status will be collected up to follow-up period (20 weeks after day 1). Death is considered as an event. All the mortality events and cause of death will be listed by treatment group and by patient. Number of patients died and survival time will be summarized by treatment group. Survival time will also be listed by patient. Risk and risk difference of all causes mortality by Day 28 and during the study period will also be summarized.

The hazard ratio will be estimated by the Cox proportional hazards model with treatment group as a covariate in the model. Relevant hazard rates, hazard ratio between treatment groups and associated p-values will be tabulated.

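### Section 12.2 analyses change in the raw P(A-a)O2 gradient whatever the oxygen setting at each visit, although 4.1 and 5.1 promise to normalise for supplemental oxygen

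*Protocol*

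**What the plan says.** Section 4.1 makes the gradient and the PaO2/FiO2 ratio the two primary oxygenation measures. On sampling it says: "Preferentially, this measurement should be done in the upright position, while breathing room air for a minimum of 3 minutes". If oxygen cannot be stopped, FiO2 and the delivery method are recorded, "so that A-a gradient can be normalized for age expected normal A-a gradient while on supplemental oxygen use". Section 5.1 makes the same promise: "if needed A-a gradient will be normalized against expected age- and supplemental oxygen dependent A-a gradient". Section 9.2 gives a table that turns device and flow into an estimated FiO2 (nasal: 24, 28, 32, 36, 40 and 44%). No section requires the same FiO2 on Day 1 and Day 6.

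Section 4.1 counts patients who improve in gradient and ratio "between day 6 and day 1 of at least 25%; at least 33% and at least 50% in each treatment arm".

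Section 12.2 does the following:
- It defines the gradient by the alveolar gas equation with a respiratory quotient of 0.8.
- It compares change from baseline between groups A and B by t-test, and names a Chi-square test for improvement in oxygenation.
- It summarises "At least 25% reduction from baseline, at least 33% reduction from baseline, and at least 50% reduction from baseline" in the gradient and in a *pathological* gradient. PaO2/FiO2 is not part of that sentence.
- It fixes one normal value ("The normal value of AA gradient for room air is calculated as" 2.5 + 0.21 x age), to be listed with a Day 6 abnormality flag. The *pathological* gradient is not defined.

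**The concern.** The gradient contains FiO2 directly, so it moves when the oxygen setting moves, even if the lungs do not. Sections 4.1 and 5.1 recognise this and promise an oxygen-dependent reference. The analyses stated in 12.2 use the gradient without it, and the one reference printed there applies to room air.

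Differing settings are to be expected. One entry route is saturation below 93% on at least 2 l/min of oxygen, so some patients start oxygen-dependent. A value from the day of discharge replaces Day 6 for those who leave early, and recovering patients may be off oxygen by then.

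What is at stake is how one of the two primary measures is read. A patient could count as a gradient responder because the flow was turned down, and one whose ratio improved on more oxygen could count as worse. Treating staff know the allocation and set the oxygen.

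**Working it through.** The plan prints no figure for this effect, so the check starts from its own formula.

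**Inputs.** From the protocol: the gradient formula, the normal value 2.5 + 0.21 x age and the thresholds (12.2); the nasal FiO2 table (9.2); the entry limit PaO2/FiO2 < 350 (6.1), so ratios of 250 and 300 are eligible. Assumed, because the protocol does not give them: atmospheric minus water-vapour pressure 760 - 47 = 713 mmHg; PaCO2 35 mmHg, with 40 as a check.

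**Formula.** Write R for PaO2/FiO2 in mmHg, so PaO2 = FiO2 x R. Then gradient = FiO2 x (713 - R) - PaCO2/0.8. At PaCO2 35 the last term is 43.75. With R fixed, the gradient is linear in FiO2.

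**Two steps down, R = 250 at both visits** (nasal 4 to 2 l/min, FiO2 0.36 to 0.28):
- Day 1: 0.36 x 463 - 43.75 = 122.9
- Day 6: 0.28 x 463 - 43.75 = 85.9
- Change -30%. The ratio changes by 0%.

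**FiO2 0.28 to room air, R = 300 at both visits:**
- 0.28 x 413 - 43.75 = 71.9, then 0.21 x 413 - 43.75 = 43.0
- Change -40%. The ratio changes by 0%.

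**Opposite direction, FiO2 0.28 to 0.40 with R rising from 200 to 250:**
- 0.28 x 513 - 43.75 = 99.9, then 0.40 x 463 - 43.75 = 141.5
- Change +42%, scored as worse although the ratio is 25% higher.

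With PaCO2 40 the three changes are -32%, -44% and +44%.

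**Single adjacent steps, R = 250, PaCO2 35:**

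| FiO2 step | Gradient change |
|---|---|
| 0.44 to 0.40 | -11.6% |
| 0.40 to 0.36 | -13.1% |
| 0.36 to 0.32 | -15.1% |
| 0.32 to 0.28 | -17.7% |
| 0.28 to 0.24 | -21.6% |
| 0.24 to 0.21 | -20.6% |

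None reaches 25%. At the edge of the assumptions (R = 300, PaCO2 40) the step 0.28 to 0.24 just does: 0.04 x 413 / (0.28 x 413 - 50) = 16.52/65.64 = 25.2%.

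**Room-air normal subtracted.** If, and only if, the *pathological* gradient is the gradient minus 2.5 + 0.21 x age, then at age 60 the normal is 15.1. The first two examples become (122.9 - 15.1) to (85.9 - 15.1), -34%, and (71.9 - 15.1) to (43.0 - 15.1), -51%. Subtracting a constant from both visits enlarges the percentage change.

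**PaO2/PAO2 on the same data**, with PAO2 the bracketed term in 12.2:
- 0.36 to 0.28: 90/212.9 = 0.423 to 70/155.9 = 0.449, +6%
- 0.28 to room air: 84/155.9 = 0.539 to 63/106.0 = 0.594, +10%
- 0.28 to 0.40: 56/155.9 = 0.359 to 100/241.5 = 0.414, +15%, in the same direction as the ratio

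**A second meaning of unchanged lungs.** Hold shunt constant instead of the ratio (assumed: shunt 10 to 30%, haemoglobin 13 g/dl, arteriovenous oxygen difference 4.5 ml/dl, PaCO2 36). FiO2 0.40 to 0.32 then lowers the gradient 31 to 32%, while PaO2/FiO2 rises 4 to 19%. For a larger change, 0.40 to 0.28 at 20% shunt, PaO2 goes from 82.5 to 72.4. The gradient falls 48%, PaO2/FiO2 rises about 25%, and PaO2/PAO2 goes from 82.5/240.2 = 0.343 to 72.4/154.6 = 0.468, +36%. The FiO2-indexed measures move too, though proportionally less than the gradient.

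**The case against.** Several points on the other side stand.

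- **The joint definition.** Section 4.1 joins gradient and ratio with an *and*. If both must improve, titration at a constant ratio makes no responder there. A reader might infer that oxygen titration alone creates primary-endpoint responders in general; the text does not support that. Two analyses remain exposed under either reading: the gradient-only responders and the gradient t-test in 12.2. The joint definition is not fully immune at constant shunt, but it takes a large FiO2 change to show it.
- **How much of the change is oxygen setting.** A reader might infer most of it. That needs the spread of the changes in FiO2, PaO2 and PaCO2, which the protocol does not give. With assumed spreads the share runs from 56% to 96%, so no figure can be claimed.
- **No between-arm effect is shown.** Nothing in the protocol says the arms would be weaned differently, and the number of patients with differing FiO2 is unknown. The preference for room-air gases reduces it.
- **PaO2/FiO2 is not the truth.** It also depends on FiO2, and needing less oxygen at the same PaO2 is real improvement.
- **The SAP is not at hand.** It may define the *pathological* gradient and an oxygen-dependent normal. So it cannot be said that the room-air constant is subtracted from on-oxygen values, and the -34% and -51% are conditional. What remains is in the protocol itself: 12.2 states raw-gradient analyses and a room-air normal that do not match 4.1 and 5.1.

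**Conclusion.** The concern holds in a limited form. The normalisation promised in 4.1 and 5.1 is not carried into the raw-gradient t-test and gradient-only responder counts of 12.2, so those results partly reflect the oxygen setting. At a constant PaO2/FiO2, two nasal-table steps move the gradient by about the 25% threshold or more (30% for 0.36 to 0.28; 40 to 32% is borderline, 25.0% at a ratio of 150 and PaCO2 36). Going from 0.28 to room air moves it 40%. Single steps usually stay below the threshold.

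If oxygen is titrated alike in both arms, this is noise in a trial of 40 per arm. If weaning or room-air testing differs by arm, which open-label treatment allows, it becomes bias. The size of any bias cannot be derived from the document.

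The figures rest on 713 mmHg, PaCO2 of 35 to 40 mmHg, and constant PaO2/FiO2 as the meaning of unchanged lungs. The constant-shunt check leads to the same conclusion for the gradient. This should be fixed. It does not invalidate the primary endpoint, because PaO2/FiO2 is analysed beside the gradient.

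**What to change.** Reconcile 4.1 and 5.1 with 12.2 as follows.

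1. Add PaO2/PAO2 beside PaO2/FiO2 and compute both for every patient in the analysis population, not only for those whose FiO2 changed. Where FiO2 differs between visits, rest the oxygenation conclusion on these measures.
2. Keep raw gradient change and the gradient-only 25/33/50% responders as supportive, shown with Day 1 and Day 6 FiO2 by arm. Any subset with equal FiO2 at both visits is descriptive only: it is selected on a post-randomisation variable that treatment may affect.
3. Do not apply the room-air normal or the abnormality flag to gases taken on oxygen. Define the *pathological* gradient accordingly, or cite the SAP section that does.
4. State whether the 4.1 responder must improve on both measures or on either.

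**Cost.** Wording in 4.1, 5.1 and 12.2 and one more derived variable; FiO2, PaO2 and PaCO2 are already collected. The gradient carries less weight. PaO2/PAO2 and PaO2/FiO2 are less affected by FiO2, not free of it, which is why FiO2 by arm must be reported. Version 4.0 dates from June 2021 and the trial is open-label, so the change should be dated and its timing relative to data access recorded.

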12.3. Statistical analysis team

The statistical analysis will be performed by EffectStats LLC, Cambridge Massachusetts, USA, under guidance of [name], statistician.

13. Data handling

13.1. Method of data collection

Subjects that are included in the study, will be assigned a unique study number upon their registration in REDCap. On all documents submitted to the coordinating center, sponsor or CI, patients will only be identified by their study number. The subject identification list will be safeguarded by the site. The name and any other directly identifying details will not be included in the study database.

13.1.1. Case Report Form

An electronic data capture (EDC) system, i.e. REDCap, will be used for data collection. Data reported on each eCRF should be consistent with the source data. If information is not known, this must be clearly indicated on the eCRF. All missing and ambiguous data will be clarified.

Only the data required by the protocol are captured in the eCRF. The eCRFs and the database will be developed, based on the protocol. The final eCRF design will be approved by the Co-ordinating Investigator.

All data entries and corrections will only be performed by study site staff, authorized by the investigator. Data will be checked by trained personnel (monitor, data manager) and any errors or inconsistencies will be clarified. The investigator must verify that all data entries in the eCRF are accurate and correct.

REDCap is provided and maintained by Vanderbilt University; a license for use was granted to the Health, Innovation and Research Institute (HIRUZ). REDCap is a web-based system. The study site staff is responsible for data entry in REDCap.

13.1.2. Data directly collected in the CRF (no source available)

N.A.

13.2. Data storage

The data is accessed through a web browser directly on the secure REDCap server. The server is hosted within the UZ Ghent campus and meets hospital level security and back-up requirements.

Privacy and data integrity between the user's browser and the server is provided by mandatory use of Transport Layer Security (TLS), and a server certificate issued by TERENA (Trans-European Research and Education Networking Association). All study sites will have access to REDCap. Site access is controlled with IP restriction.

13.3. Archiving of data

The investigator and sponsor specific essential documents will be retained for at least 25 years. At that moment, it will be judged whether it is necessary to retain them for a longer period, according to applicable regulatory or other requirement(s).

13.4. Access to data

Direct access will be granted to authorised representatives from the Sponsor, host institution and the regulatory authorities to permit study-related monitoring, audits and inspections.

Login in REDCap is password controlled. Each user will receive a personal login name and password and will have a specific role which has predefined restrictions on what is allowed in REDCap. Furthermore, users will only be able to see data of subjects of their own site. Any activity in the software is traced and transparent via the audit trail and log files.

For access to the pseudonymized data needed for statistical analysis, a separate data transfer agreement is in place between UZGhent and EffectStats LLC. UZGhent owns the data, and the results of the statistical analysis, and EffectStats LLC is not allowed to share these data with third parties. Data generated at the VIB Center for Inflammation research (results of ELISA analysis, results of flow cytometry analysis) remain property of UZ Ghent.

14. Safety

14.1. Definitions

Term	Definition
Adverse Event (AE)	Any untoward medical occurrence in a subject to whom a medicinal product has been administered, including occurrences which are not necessarily caused by or related to that product.
Unexpected Adverse Event	An adverse event, the nature or severity of which is not consistent with the applicable product information (e.g., Investigator's Brochure for an unapproved investigational product or package insert/summary of product characteristics for an approved product).
Adverse Reaction (AR)	
An untoward and unintended response in a subject to an investigational medicinal product which is related to any dose administered to that subject.
 
The phrase "response to an investigational medicinal product" means that a causal relationship between a study medication and an AE is at least a reasonable possibility, i.e. the relationship cannot be ruled out.
 
All cases judged by either the reporting medically qualified professional or the Sponsor as having a reasonable suspected causal relationship to the study medication qualify as adverse reactions.

Serious Adverse Event (SAE)	
A serious adverse event is any untoward medical occurrence that:
 
 • results in death • is life-threatening • requires inpatient hospitalisation or prolongation of existing hospitalisation • results in persistent or significant disability/incapacity • consists of a congenital anomaly or birth defect 
Other 'important medical events' may also be considered serious if they jeopardise the subject or require an intervention to prevent one of the above consequences.
 
NOTE: The term "life-threatening" in the definition of "serious" refers to an event in which the subject was at risk of death at the time of the event; it does not refer to an event which hypothetically might have caused death if it were more severe.

Serious Adverse Reaction (SAR)	An adverse event that is both serious and, in the opinion of the reporting Investigator, believed with reasonable probability to be due to one of the study treatments, based on the information provided.
Suspected Unexpected Serious Adverse Reaction (SUSAR)	
A serious adverse reaction, the nature and severity of which is not consistent with the information about the medicinal product in question set out:
 
 • in the case of a product with a marketing authorisation, in the summary of product characteristics (SmPC) for that product • in the case of any other investigational medicinal product, in the investigator's brochure (IB) relating to the study in question

Attribution definitions

An adverse event is considered associated with the use of the drug if the attribution is possible, probable or definitive.

Not related

An adverse event which is not related to the use of the drug.

Unlikely

An adverse event for which an alternative explanation is more likely - e.g. concomitant drug(s), concomitant disease(s), and/or the relationship in time suggests that a causal relationship is unlikely.

Possible

An adverse event which might be due to the use of the drug. An alternative explanation - e.g. concomitant drug(s), concomitant disease(s), - is inconclusive. The relationship in time is reasonable; therefore the causal relationship cannot be excluded.

Probable

An adverse event which might be due to the use of the drug. The relationship in time is suggestive (e.g. confirmed by dechallenge). An alternative explanation is less likely - e.g. concomitant drug(s), concomitant disease(s).

Definitely

An adverse event which is listed as a possible adverse reaction and cannot be reasonably explained by an alternative explanation - e.g. concomitant drug(s), concomitant disease(s). The relationship in time is very suggestive (e.g. it is confirmed by dechallenge and rechallenge).

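### Section 14.1 contradicts itself on what counts as a SAR and a SUSAR, so it is unclear which serious reactions fall under the 7- and 15-day reporting limits

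*Protocol*

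**What the plan says.** Four parts of Section 14.1 bear on this.

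- **Adverse reaction.** The causal link must be "at least a reasonable possibility, i.e. the relationship cannot be ruled out". A case qualifies when it is "judged by either the reporting medically qualified professional or the Sponsor as having a reasonable suspected causal relationship".
- **Serious adverse reaction (SAR).** The event must be serious and, "in the opinion of the reporting Investigator, believed with reasonable probability to be due to one of the study treatments".
- **Unexpected adverse event.** This is an event "the nature or severity of which is not consistent with the applicable product information". The SUSAR row reads differently: "A serious adverse reaction, the nature and severity of which is not consistent with the information about the medicinal product in question".
- **Attribution rule** (below the table). "An adverse event is considered associated with the use of the drug if the attribution is possible, probable or definitive". The 'possible' category is then described as one in which causality cannot be excluded.

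The reporting rules that use these labels are in 14.2.2 to 14.7.

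- **14.2.2:** every SAE goes within 24 hours to the local ethics committee, the sponsor's trial unit (HIRUZ CTU), the national coordinating investigator and the company supplying the drug, whatever its causality.
- **14.2.3:** the coordinating investigator, together with the trial unit, decides whether an SAE is a SUSAR. Only SUSARs carry the 7- and 15-day limits, and only SUSARs are passed to the other local principal investigators.
- **14.4:** SARs and SUSARs go to the central ethics committee; only SUSARs go to the competent authority (FAMHP). Other SAEs join a yearly list.
- **14.7:** the annual safety report covers SAEs that were not classed as SARs.

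**The concern.** These are operative definitions. The label given to a serious event decides whether the authority hears of it in days or through an annual report. The SAR and SUSAR rows are narrower than the adverse-reaction and unexpected-event rows on three points: the causal threshold, who may judge it, and whether nature and severity must both be unexpected. Because the SUSAR row starts from a serious adverse reaction, the first two narrowings can carry over into it.

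The events at stake are plausible ones here. Section 2.3 states that there are no safety data for this drug in COVID-19. The patients have acute hypoxic respiratory failure, so the disease will often be a competing explanation and 'possible' a natural rating. Section 8.1.8 lists bronchospasm among the effects seen with the aerosolised drug. If bronchospasm is also in the reference product information (an assumption, since that text is not shown), an unusually severe case would have a labelled nature but a severity beyond the label.

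**Working it through.** No arithmetic decides this point, so the check sets the texts side by side and runs three cases through them.

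**The texts compared (all in 14.1)**

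| Element | Broader wording | Narrower wording |
|---|---|---|
| Causal threshold | Adverse reaction: a possibility that cannot be excluded; attribution 'possible' counts | SAR: reasonable probability |
| Who judges | Adverse reaction: reporter or sponsor, either suffices | SAR: reporting investigator |
| Unexpectedness | Unexpected event: nature or severity | SUSAR: nature and severity |

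**Three serious events, taken literally**

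1. *Unexpected in both nature and severity, rated 'possible' by the investigator.* It is an adverse reaction and counts as associated with the drug. It need not reach reasonable probability, so it need not be a SAR, and hence need not be a SUSAR. It then stays an SAE: reported within 24 hours under 14.2.2, and otherwise placed on the yearly list.
2. *Unexpected in both nature and severity, judged unrelated by the investigator but suspected by the sponsor.* It is an adverse reaction through the sponsor's judgement. The SAR row gives the sponsor's judgement no weight. The outcome is as in case 1.
3. *Judged probably related by the investigator, of labelled nature but greater than labelled severity.* It is a SAR, and it is unexpected by the 'or' test. It fails the 'and' test of the SUSAR row. Under 14.4 it still goes to the central ethics committee as a SAR, but no step to the FAMHP is listed, and the stated content of the annual report in 14.7 does not name it.

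Under the broader wording all three are serious, related and unexpected, and so are SUSARs. Under the narrower wording none has to be.

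**What turns on the label**

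- SUSAR: 7 calendar days if fatal or life-threatening, otherwise 15 (14.2.3).
- SAE not classed as a SAR: the annual report. The first is due at most 1 year plus 60 days after the Development International Birth Date, that is 365 + 60 = 425 days. This runs from the birth date and not from the event, so it is an outer limit for the first report and not a typical delay. Reports can also be requested earlier (14.7).

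**Does another section settle it?** Section 14.2.3 says who decides but states no criteria for causality or unexpectedness. The person deciding is left with 14.1.

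**The case against.** The strongest reply is that the operating procedure protects against the wording. Every SAE reaches the trial unit and the coordinating investigator within 24 hours. The SUSAR decision is taken centrally and starts from the SAE, not from the site's SAR label. The only rule linking the attribution scale to relatedness already counts 'possible', and nothing equates reasonable probability with the 'probable' category. The SUSAR row can be read as an adverse reaction that happens to be serious, and its 'and' can be read as satisfied when either element is inconsistent.

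Most of this stands, and it rules out stronger readings that a reader might infer:

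- *That these events are certain to go unreported on an expedited basis, or can never be classed as SUSARs.* The documents do not support this. A central decision could apply the broader wording and classify all three cases as SUSARs.
- *That ethics committees are left uninformed.* The local committee receives every SAE within 24 hours, and case 3 also goes to the central committee as a SAR. The exposed routes are the 7- and 15-day submissions to the FAMHP and the central committee, and the notice to other sites.
- *That a given share of drug-related serious events would be lost.* The protocol offers no basis for a share. Only unexpected reactions were ever subject to the 7- or 15-day limits, so all drug-related serious events would be the wrong denominator.

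Section 14.5 also keeps several natural-course events, such as progression to ARDS or multi-organ failure, from being reported as adverse events. Rewording the SAR and SUSAR rows would not change that.

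The reply does not resolve the conflict. Central classification helps only if the person classifying has one rule to apply, and 14.1 supplies two. Receipt by the trial unit is not submission to the authority.

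**Conclusion.** Wrong as written: an internal contradiction in 14.1 that carries into 14.2.3 and 14.4. It is unclear whether serious unexpected reactions that are rated 'possible', suspected only by the sponsor, or of labelled nature but greater severity must be handled as SUSARs. On a literal reading they can fall outside the definition, and so outside the 7- and 15-day submission and the notice to other local investigators.

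This rests on the wording alone. No event is shown to have been missed, and the number that might be affected cannot be derived from the protocol. The 24-hour SAE route and central classification limit the harm but leave the ambiguity in place. Because it concerns what must reach the authority within days, it should be corrected. It has no bearing on sample size, error rates or the efficacy analysis.

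**What to change.** Reconcile 14.1 with 14.2.3 using the protocol's own broader wording:

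1. Define a SAR as an adverse reaction, as already defined in 14.1, that meets a seriousness criterion. This brings in both the lower causal threshold and the either-party judgement.
2. In the SUSAR row, replace 'and' with 'or' between nature and severity, to match the unexpected-event row.
3. In 14.2.3, state that classification follows these definitions and that an attribution of 'possible' or higher, by the investigator or the sponsor, counts as related.

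The cost is a few sentences in an amendment and a few more expedited reports. No data collection or analysis changes.
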